5.3 SAMPLES FOR GENETIC/GENOMIC ANALYSIS

5.3.1 Description of the scope of genetic/genomic analysis

- Myeloid mutation molecular analysis – Next Generation Sequencing (NGS):
 - Bone marrow aspirate and peripheral blood samples will be sent for NGS as discussed in clinical monitoring section above.
 - These will detect mutations and report respective variable allele frequency which will help support whether the mutations are somatic versus germline. With any concern for germline mutation, further testing will be supported for confirmation.
 - As NGS analysis is for clinical purposes and is being performed by a CLIA-certified clinical laboratory, NGS results may be added to the medical record and returned to the participant to help inform future therapy.
 - Research whole genome sequencing, Single cell sequencing, Ultra-deep NGS measurable residual disease mutational analysis.
 - Genetic Biomarkers:
 - IL-8 is a stimulator of angiogenesis, which acts through the receptors CXCR1 and CXCR2, the latter being the endothelial receptor. The IL-8 -251T > A polymorphism increases plasma IL-8 levels by increasing IL-8 production[\[114\]](#) [\[96\]](#) Single nucleotide polymorphisms (SNPs) the IL-8/CXCR1/CXCR2 genes could alter treatment response or outcome by affecting the IL-8 signaling pathway.
 - This will be assessed via WGS studies, and correlation between these genetic variants and toxicity and clinical endpoints will be explored.
 - Germline-predisposition to MDS evaluation:
 - All participants will receive a careful medical and clinical evaluation with particular focus on indicators of possible germline predisposition. Where appropriate, especially for participants diagnosed with MDS under the age of 40 years or with a strong family history, germline testing for mutations in genes predisposing to myeloid malignancy will be obtained via skin biopsy and culturing of fibroblasts.
 - For positive cases, referral to clinical protocols at NIH and elsewhere will be made after discussion with individual participants about available treatment options.

5.3.2 Description of how privacy and confidentiality of medical information/biological specimens will be maximized

NGS analysis will be both for clinical and research purposes. Results of NGS testing performed by a CLIA-certified clinical laboratory will be added to the medical record and returned to the participant to help inform future therapy. Research sequencing results will not be returned to participants, unless a potentially actionable clinically actionable gene variant is identified (see 5.3.3). If a germline mutation is found upon further testing, participant will be referred to genetic counseling. PHI will be linked to the sample as this is an important part of disease management and prognostication and is standard. PHI will not be released to third parties. Research sequencing will be uploaded to public databases in compliance with NIH genomic data sharing policies.

5.3.3 Management of Results

Subjects will be contacted if a clinically actionable gene variant is discovered. Clinically actionable findings for the purpose of this study are defined as disorders appearing in the American College of Medical Genetics and Genomics recommendations for the return of incidental findings that is current at the time of primary analysis. Subjects will be contacted at this time with a request to provide a sample to be sent to a CLIA certified laboratory. If the research findings are verified in the CLIA certified lab, the subject will be offered the opportunity to come to NIH (at our expense) to have genetic education and counseling to explain this result. If the subject does not want to come to NIH, a referral to a local genetic healthcare provider will be provided (at their expense).

This is the only time during the course of the study that incidental findings will be returned. No interrogations regarding clinically actionable findings will be made after the primary analysis.

6 DATA COLLECTION AND EVALUATION

6.1 DATA COLLECTION

The PI will be responsible for overseeing entry of data into a 21 CFR Part 11-compliant data capture system provided by the NCI CCR and ensuring data accuracy, consistency and timeliness. The principal investigator, associate investigators/research nurses and/or a contracted data manager will assist with the data management efforts. Primary and final analyzed data will have identifiers so that research data can be attributed to an individual human subject participant.

All adverse events, including clinically significant abnormal findings on laboratory evaluations, regardless of severity, will be followed until return to baseline or stabilization of event.

Document AEs from the first study intervention, study day 1, through study day 100 after the subject received the last product administration, except for Grade 1 AEs, which will be collected and recorded for first 30 days on study only. After 100 days, only adverse events which are serious and related to the study investigational agent need to be recorded.

An abnormal laboratory value will be recorded in the database as an AE **only** if the laboratory abnormality is characterized by any of the following:

- Results in discontinuation from the study
- Is associated with clinical signs or symptoms

- Requires treatment or any other therapeutic intervention
- Is associated with death or another serious adverse event, including hospitalization.
- Is judged by the Investigator to be of significant clinical impact
- If any abnormal laboratory result is considered clinically significant, the investigator will provide details about the action taken with respect to the test drug and about the participant's outcome.

The PI evaluation of each AE not captured in the clinical database determining that it meets the criteria above will be documented in the source documents.

End of study procedures: Data will be stored according to HHS, FDA regulations, and NIH Intramural Records Retention Schedule as applicable.

Loss or destruction of data: Should we become aware that a major breach in our plan to protect subject confidentiality and trial data has occurred, this will be reported expeditiously per requirements in section **7.2.1**.

6.2 DATA SHARING PLANS

6.2.1 Human Data Sharing Plan

What data will be shared?

I will share human data generated in this research for future research as follows:

Coded, linked data in an NIH-funded or approved public repository.

Coded, linked data in BTRIS (automatic for activities in the Clinical Center)

Identified or coded, linked data with approved outside collaborators under appropriate agreements.

How and where will the data be shared?

Data will be shared through:

An NIH-funded or approved public repository. Insert name or names: CCR BPC.

BTRIS (automatic for activities in the Clinical Center)

Approved outside collaborators under appropriate individual agreements.

Publication and/or public presentations.

When will the data be shared?

Before publication.

At the time of publication or shortly thereafter.

6.2.2 Genomic Data Sharing Plan

Unlinked genomic data will be deposited in public genomic databases in compliance with the NIH Genomic Data Sharing Policy.

6.3 RESPONSE CRITERIA

In addition to a baseline bone marrow biopsy, bone marrow biopsy samples from the participant's previous biopsy procedures will be requested from outside institutions: a formalin-fixed paraffin-embedded (FFPE) block or 10 unstained slides from initial MDS diagnosis, and an FFPE block from the most recent MDS biopsy prior to the participant arriving at NCI. These archival samples will be used to reconfirm the MDS diagnosis by NIH pathology department.

Participants will be assessed for response by standard response criteria for MDS.[\[85\]](#) For the purposes of this study, participants will be re-evaluated for response after each cycle by CBC with differential to assess for improvement in cytopenias and by protocol-defined time points for bone marrow evaluation. If results from interim bone marrow assessment demonstrate progression of disease (as defined by an increase in the number of malignant cells or blasts when compared to pre-treatment bone marrow examination or worsening cytopenias by amounts as defined below in section [6.3.1](#)), the subject will be taken off study.

Participants with ECOG performance status of 0-2 who fail to achieve a CR but have achieved a PR, SD, or hematologic improvement will be eligible for receive additional therapy if no other contraindications to further treatment.

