3.8.1 Criteria for removal from protocol therapy

- Progressive disease
- Participant requests to be withdrawn from active therapy
- Unacceptable toxicity as (section 3.3)
- Lack of clinical response seen after 6 cycles of therapy (C7D1)
- Completion of safety visit
- Investigator discretion
- Positive pregnancy test

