6.3.1 Response Criteria

The table below shows the 2006 International Working Group response criteria for altering the natural history of MDS,[\[115\]](#) with modified definitions for HI-E, HI-P, and HI-N in the suggested 2018 International Working Group response criteria.[\[85\]](#)

Category	Response criteria (responses must last at least 4 weeks)
Complete remission	
 • Bone marrow: $\leq 5\%$ myeloblasts with normal maturation of all cell lines* • Persistent dysplasia will be noted* • Peripheral blood† 
 • Hgb ≥ 11 g/dL • Platelets $\geq 100 \times 10^9/L$ • Neutrophils $\geq 1.0 \times 10^9/L$ • Blasts 0%
Partial remission	All CR criteria if abnormal before treatment except: 
 • Bone marrow blasts decreased by $\geq 50\%$ over pretreatment but still $> 5\%$ • Cellularity and morphology not relevant
Marrow CR	
 • Bone marrow: $\leq 5\%$ myeloblasts and decrease by $\geq 50\%$ over pretreatment • Peripheral blood: if HI responses, they will be noted in addition to marrow CR

Stable disease	Failure to achieve at least PR, but no evidence of progression for >8 wks
Failure	Death during treatment or disease progression characterized by worsening of cytopenias, increase in percentage of bone marrow blasts, or progression to more advanced MDS FAB subtype than pre-treatment
Relapse after CR or PR	At least 1 of the following: 
 Return to pre-treatment bone marrow blast percentage Decrement of $\geq 50\%$ from maximum remission/response levels in granulocytes or platelets Reduction in Hgb concentration by ≥ 1.5 g/dL or transfusion dependence
Cytogenetic response	Complete 
 Disappearance of the chromosomal abnormality without appearance of new ones Partial 
 At least 50% reduction of the chromosomal abnormality
Disease progression	For participants with: 
 Less than 5% blasts: $\geq 50\%$ increase in blasts to $>5\%$ blasts 5%-10% blasts: $\geq 50\%$ increase to 10% blasts 10%-20% blasts: $\geq 50\%$ increase to $>20\%$ blasts 20%-30% blasts: $\geq 50\%$ increase to $>30\%$ blasts Any of the following: 
 At least 50% decrement from maximum remission/response in granulocytes or platelets Reduction in Hgb by ≥ 2 g/dL Transfusion dependence

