Survival	Endpoints: 
 Overall: death from any cause Event free: failure or death from any cause PFS: disease progression or death from MDS DFS: time to relapse Cause-specific death: death related to MDS

MDS, myelodysplastic syndromes; Hgb, hemoglobin; CR, complete remission; HI, hematologic improvement; PR, partial remission; FAB, French-American-British; AML, acute myeloid leukemia; PFS, progression-free survival; DFS, disease-free survival.

To convert hemoglobin from grams per deciliter to grams per liter, multiply grams per deciliter by 10.

*Dysplastic changes should consider the normal range of dysplastic changes.

†In some circumstances, protocol therapy may require the initiation of further treatment (eg, consolidation, maintenance) before the 4-week period. Such participants can be included in the response category into which they fit at the time the therapy is started. Transient cytopenias during repeated chemotherapy courses should not be considered as interrupting durability of response, as long as they recover to the improved counts of the previous course.

Hematologic Improvement

Category	Participant pre-trial baseline	Response criteria
----------	--------------------------------	-------------------

Erythroid response (HI-E)	No Transfusion Dependence at baseline (0 RBC transfusions in 16 weeks)	At least 2 consecutive Hgb measurements ≥ 1.5 g/dL for a period of minimum 8 weeks in an observation period of 16 to 24 weeks compared with the lowest mean of 2 Hgb measurements (apart from any transfusion) within 16 weeks before treatment onset; only a response duration of at least 16 weeks, however, is considered clinically meaningful
	Low Transfusion Dependence at baseline (3-7 RBC transfusions in 16 weeks in at least 2 transfusion episodes, maximum 3 in 8 weeks)	Transfusion independence, defined by the absence of any transfusions for at least 8 weeks in an observation period of 16-24 weeks with the same transfusion policy compared with 16 weeks prior to treatment; only a response duration of at least 16 weeks, however, is considered clinically meaningful

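### Section 6.3 takes participants with interim-marrow progression off study, contrary to 3.8 and the planned survival follow-up, and leaves unclear whether any blast increase counts as progression

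*Combined protocol and SAP*

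**What the plan says.** **Section 6.3 (Response Criteria).** If an interim marrow shows progression, "the subject will be taken off study". A parenthesis explains progression as "an increase in the number of malignant cells or blasts when compared to pre-treatment bone marrow examination or worsening cytopenias by amounts" defined in 6.3.1. The blast part has its own comparator, the pre-treatment marrow, and states no size.

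**Section 6.3.1, Disease progression row (repeated in Appendix D).** Blast progression depends on the baseline band. The first band is "Less than 5% blasts" and needs a rise of at least 50% to above 5%. The later bands need the same relative rise to 10%, above 20% and above 30%. Falls in counts or hemoglobin, or transfusion dependence, are separate routes to progression.

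**Other rows of 6.3.1.** The Failure row names an "increase in percentage of bone marrow blasts" without a size. Stable disease is "Failure to achieve at least PR, but no evidence of progression for >8 wks". The Survival row has "PFS: disease progression or death from MDS".

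**Section 3.8.** The list in 3.8.1 of reasons for removal from protocol therapy opens with "Progressive disease". The off-study list in 3.8.2 does not include progression. Section 2.3 treats off-therapy and off-study as different statuses.

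**Follow-up.** The schema notes in 3.1 make progression an end-of-treatment event, and 3.1 follows participants for survival until study closure. Section 3.4 schedules status calls after the End of Treatment visit for at least 5 years from enrollment. Section 10.2 ranks OS as the most important secondary endpoint.

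**The concern.** The off-study wording does not depend on how any phrase is parsed. A site that follows 6.3 would close the record of a participant whom 3.1 and 3.4 expect it to keep calling. Follow-up would then stop because of the disease course, which makes censoring of OS and LFS informative. It would also cut short PFS follow-up in anyone removed for a blast rise that does not meet the Disease progression row.

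The blast wording is a matter of reading. If the amounts in 6.3.1 apply only to the cytopenias, any blast value above pre-treatment means removal. Blast percentages come from cell counts, so an unchanged marrow can read higher the second time. In phase II the first required on-treatment marrow is at C2D28, well before the response assessment after 6 cycles. Progression also enters stable disease (hence OIR in 10.4.3) and PFS, so one definition should serve throughout.

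**Working it through.** The plan states no figure on this point, so there is none to reproduce. The check compares the sections, tries example values, and adds one illustration.

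**1. Status after progression**

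| Section | What progression leads to |
|---|---|
| 6.3 | Off study |
| 3.1, schema notes | End of treatment |
| 3.8.1 | Removal from protocol therapy |
| 3.8.2 | Not listed as an off-study reason |
| 3.1 and 3.4, follow-up | Survival status still collected after treatment |

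Section 6.3 stands alone. Investigator discretion does appear in 3.8.2, but it is not a rule about progression.

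**2. Blast rule: any increase against the Disease progression row**

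Relative rise = (follow-up − baseline) / baseline.

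| Baseline to follow-up | Relative rise | Any increase | Blast part of the row |
|---|---|---|---|
| 2% to 3% | 1/2 = 50% | yes | no: 3% is not above 5% |
| 6% to 8% | 2/6 = 33% | yes | no: below 50%, and below 10% |
| 12% to 18% | 6/12 = 50% | yes | no: 18% is not above 20% |
| 3% to 6% | 3/3 = 100% | yes | yes |
| 8% to 12% | 4/8 = 50% | yes | yes |

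The smallest follow-up values that meet the row are: baseline 2% or 3%, just over 5%; 4%, 6%; 6%, 10%; 8%, 12%; 12%, just over 20%; 15%, 22.5%.

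**3. Timing in phase II**

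With 28-day cycles, C2D28 is day 2 × 28 = 56 and C6D28 is day 6 × 28 = 168. The gap is 168 − 56 = 112 days, or four cycles.

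**4. Counting-noise illustration (assumptions, not plan figures)**

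Assume n = 200 or 500 cells per marrow and a true blast fraction p that does not change. Let X (baseline) and Y (C2D28) be independent Binomial(n, p) counts. Then P(any increase) = Σₓ P(X = x) · P(Y > x). P(row met) sums the same products over pairs with Y ≥ 1.5X and Y at the cut-off for the baseline band. All pairs were enumerated for p = 2% to 12% in half-point steps.

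| Quantity, unchanged blasts | Unrounded | Whole percent |
|---|---|---|
| Any increase, n = 200 | 42.8–46.9% | 36.0–43.9% |
| Any increase, n = 500 | 45.5–48.1% | 29.2–40.5% |
| Row met, n = 200 | 0.2–14.1% | 0.2–13.9% |
| Row met, n = 500 | 0.0–6.9% | 0.0–9.2% |
| Increase without meeting the row, both n | 31–47% | 27–40% |

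The result depends on the assumed course and range of blasts:

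- If true blasts have fallen by a quarter, P(any increase) is 5.4–28.1% unrounded and 3.7–22.4% in whole percent.
- If they have fallen by half, it is 0.0–14.6% and 0.0–10.7%.
- Below the grid, with unchanged blasts in whole percent, it is 30.6% (n = 200) and 20.7% (n = 500) at p = 1%, and 27.7% and 25.0% at p = 0.5%. Unrounded at p = 1% with n = 200 it is 39.6%.

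The lower values matter because the lowest IPSS-R blast band in Appendix C is 2% or less, and one cohort is lower-risk.

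**The case against.** **The reference to 6.3.1 can cover both parts.** The trigger in 6.3 is progression of disease, and 6.3.1 has a row with that title which sizes both blasts and cytopenias. The same section says that response follows standard MDS criteria, and its next paragraph lets participants with stable disease continue. An any-increase rule fits that poorly. The Failure row does not decide the matter, because its cytopenia wording is unsized too and may be shorthand. This stands to the extent that a reader who infers a plain contradiction between 6.3 and 6.3.1 goes further than the text. It does not remove the ambiguity: the blast part carries its own comparator and no size, and nothing elsewhere settles the reading.

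**Section 3.8 and the follow-up text already govern.** Most of the protocol does point the right way, and a careful site would probably follow it. But 6.3 gives an explicit instruction to the contrary, and the protocol does not say which section prevails.

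**The illustration is not evidence of impact.** This stands. Cell counts, binomial error, unchanged disease and mechanical use of the rule are all assumed. A reader might infer that 29–48% of participants would be removed, and the documents do not support that.

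**Stable disease at C2D28.** A reader might also see a direct clash with the stable-disease rule at this visit. That row needs more than 8 weeks, and C2D28 is day 56 ± 3, so no such clash is claimed.

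**Conclusion.** The off-study wording in 6.3 is inconsistent with 3.8.1, 3.8.2, 3.1 and 3.4 on any reading. Taken literally, it ends OS, LFS and PFS follow-up in participants who progress. The blast wording is an ambiguity in a removal rule. One available reading removes participants who do not meet the Disease progression row, as early as four cycles before C6D28 in phase II.

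The size of the effect cannot be drawn from the documents. The counting-noise ranges show only that the two readings can differ often under the stated assumptions.

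A reader might infer a lower ORR, lost power or faulty stopping boundaries, and none of these is supported. The documents give neither the number who would be removed nor how many of them would later have responded. The Simon designs do not use this rule: exact binomial calculation gives alpha 0.0997, power 0.804 and early-termination probability 0.722 for the higher-risk cohort, and 0.0991, 0.815 and 0.558 for the lower-risk cohort, in agreement with 10.2.

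The wording should be corrected; the design does not need to change.

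**What to change.** In 6.3, replace the parenthesis with: *as defined in the Disease progression row of section 6.3.1*. In the same sentence, change the consequence from off study to *taken off protocol therapy*.

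Optionally, add a sentence to 6.3.1 and Appendix D stating that the same row defines progression for stable disease (hence OIR) and for PFS. Leave the Failure row as it is. It also lists a move to a more advanced FAB subtype, which the Disease progression row does not, and the event-free endpoint it feeds ("Event free: failure or death from any cause") is not among the endpoints in 10.1 or the analyses in 10.4.3. Tying the two rows together would change content.

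The cost is a wording amendment, with no extra data, visits or participants.

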3 STUDY IMPLEMENTATION

3.1 STUDY DESIGN

This study consists of two phases:

- Phase I: determination of OBD of BMS-986253 with and without DNMTi for HR- and LR-MDS cohorts, respectively, and
- Phase II: examining the efficacy of BMS-986253 with and without DNMTi for HR- and LR-MDS cohorts, respectively

In the Phase I, subjects will be enrolled to start treatment with BMS-986253 after a minimum of 2 cycles and up to initiation of an 8th cycle of DNMTi.

The safety endpoint will be DLT on D28. In addition, follow up for safety will be assessed 100 days after the last dose of treatment.

OBD will be the lowest tolerated dose level showing optimal biological activity, defined as maximal suppression of serum free IL-8 levels.

Participants enrolled on phase I will be treated at the corresponding BMS-986253 dose level until occurrence of disease progression, death, or unacceptable toxicity or until response assessment on C7D1 (maximum 6 cycles) if no evidence of clinical response. The participants will be followed up for overall, event- and progression-free survival until the study closure. The study will be closed when all enrolled participants have been followed up for at least 8 years or have died.

[figure not shown]
Both Phase I and II portions of study will enroll two cohorts:

A) HR-MDS: subjects with higher-risk MDS that will be treated with BMS-986253 in combination with DNMTi.

B) LR-MDS: subjects with lower-risk MDS that will be treated with BMS-986253 given as monotherapy.

In the Phase II portion, the treatment naïve subjects (or up to 4 cycles of prior DNMTi) will start treatment with BMS-986253 from the first cycle and the efficacy will be assessed until any off-treatment criteria are met (Section 3.8). BMS-986253 will be administered on days 1 and 15 of each cycle, and participants will remain on therapy until disease progression, death, or unacceptable toxicity or taken off therapy if no evidence of clinical response after 6 cycles (C7D1). The participants will be followed up for overall, event- and progression-free survival until the study closure. The study will be closed when all enrolled participants have been followed up for at least 5 years or have died.

Study treatment schema

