3.8.2 Off-Study Criteria

- Participant requests to be withdrawn from study
- Death
- Screen failure
- Permanent loss of capacity to consent
- Completion of protocol-driven follow-up
- Lost to follow-up
- Investigator discretion

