Phase II: To evaluate safety and secondary clinical outcomes of BMS-986253 in MDS participants by cohort.	-Safety, as measured by: Incidence of AEs, SAEs; and AEs leading to discontinuation, death, and laboratory abnormalities, assessed from first cycle until time of disease relapse, disease progression, or death, whichever occurs first, assessed every 3-6 months - Clinical outcomes including: overall improvement rate (OIR), cytogenetic response rate, time to best response (CR, PR, marrow CR, or HI), disease free survival (DFS; definition: time to relapse for participants who achieve CR), progression free survival (PFS; definition: disease progression or death from MDS), leukemia free survival (LFS; definition: progression to AML or death from any cause), and overall survival (OS; definition:	Confirm safety and evaluate efficacy through long-term clinical outcomes

OBJECTIVES	ENDPOINTS	JUSTIFICATION FOR ENDPOINTS
	death from any cause); assessed every 3-6 months	
Exploratory		
To evaluate changes in serum cytokine levels pre- and post-treatment with BMS-986253.	Each of these will be evaluated using descriptive methods and reported as exploratory results. If any statistical tests are performed in these analyses, the results will be presented without adjustment for multiple comparisons but reported in the context of the number of tests performed. See section 5 for collection timepoints.	Evaluate mechanistic and immunologic effects of the study drug
To evaluate the cell composition in the peripheral blood and bone marrow microenvironment before and after treatment with BMS-986253.		
To evaluate changes in the transcriptome and proteome in response to treatment with BMS-986253.		
To determine the degree of bone marrow myeloid-derived suppressor cell (MDSC) infiltration.		
To describe changes in genetic clonal diversity during treatment with BMS-986253 in combination with DNMTi.		
To assess cell-autonomous effects on the MDS clone by measuring biomarkers in the Akt pathway (i.e. pS743) in MDS blasts.		
To evaluate cell-autonomous and microenvironment dependent activity of BMS-986253 using ex vivo culture of participant-derived		

OBJECTIVES	ENDPOINTS	JUSTIFICATION FOR ENDPOINTS
hematopoietic stem and progenitor cells.		
To assess quality of life improvement by participant reported outcomes using the EORTC QLQC30 score.		

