- In participants with low-risk MDS, the trial will be conducted using a Simon optimal two-stage phase II trial design to rule out an unacceptably low response rate (CR+PR+mCR with HI) of 20% ($p_0=0.20$) in favor of an improved response rate of 40% ($p_1=0.40$) in order to determine if monotherapy with BMS-986253 will be able to improve upon an expected response rate below 30% in participants who have received other agents. [76, 83, 84] With $\alpha=0.10$ (probability of accepting a poor treatment=0.10) and $\beta=0.20$ (probability of rejecting a good treatment=0.20), the first stage will enroll 12 evaluable participants, including the 6 participants from the phase I dose escalation, that reached MTD, and if 0 to 2 of the 12 has a response, then no further participants will be accrued. If 3 or more of the first 12 participants has a response, then accrual would continue until a total of 25 evaluable participants have been treated in that cohort. As it may take up to several months to determine if a participant has experienced a response, a temporary pause in the accrual may be necessary to ensure that enrollment to the second stage is warranted. If there are only 3-7 participants with a response out of 25 participants, this would be an uninterestingly low response rate. If there were 8 or more of 25 (32.0%) who experienced a response, treatment in the appropriate cohort would be sufficiently interesting to warrant further study in later trials. Under the null hypothesis (20% response rate), the probability of early termination is 55.8%.

Secondary endpoints include progression free survival, overall survival, median survival, duration of response, and leukemia free survival. These will be determined separately in each of the phase II cohorts. Overall survival is considered an important endpoint in these participants and will be considered the most important secondary endpoint.

It is expected that up to 12-15 participants with MDS may be accrued per year. Thus, in order to accrue up to $18+18+32+25 = 93$ participants, it is expected that 4-5 years may be required to accrue the total number of required evaluable participants. In order to allow for a small number of inevaluable participants and potentially large number of screen failures, the accrual ceiling will be set at 200 participants.

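### Section 6.3 takes participants off study at marrow progression, against the protocol's own off-study list and follow-up plan, and the phase II safety window in 10.1 does not match the 100-day window

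*Combined protocol and SAP*

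**What the plan says.** **Status at progression.** Section 6.3 states that if an interim marrow assessment shows progression, by rising blasts or by worsening cytopenias, "the subject will be taken off study". Section 3.8 keeps two lists. The off-therapy list (3.8.1) includes "Progressive disease". The off-study list (3.8.2) covers withdrawal, death, screen failure, loss of capacity to consent, "Completion of protocol-driven follow-up", loss to follow-up and investigator discretion, and it does not include progression. Section 2.3 also treats leaving protocol therapy and leaving the study as separate status updates.

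**Follow-up after treatment.** Section 3.1 says: "The participants will be followed up for overall, event- and progression-free survival until the study closure". Section 3.4 sets an End of Treatment visit, then phone calls every 3 months for 24 months and every 6 months after that, to at least 5 years. Appendix F collects vital status, MDS progression, secondary-AML diagnosis and date, and later MDS/AML treatment.

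**Rank of OS.** Section 10.2: "Overall survival is considered an important endpoint in these participants and will be considered the most important secondary endpoint". Section 10.4.3 analyses OS and LFS by Kaplan-Meier, with no progression cut-off.

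**Safety window.** The phase II safety endpoint in Section 10.1 is "assessed from first cycle until time of disease relapse, disease progression, or death, whichever occurs first, assessed every 3-6 months". Section 6.1 documents adverse events "through study day 100 after the subject received the last product administration" (grade 1 events only for the first 30 days on study). Section 3.8 asks for a safety visit about 100 days after the last dose, and Section 8.5 uses 100 days for serious events. None of these three makes an exception for progression.

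**The concern.** Section 6.3 is an instruction to staff, and Section 3.8.2 leaves room for investigator discretion, so a team could act on 6.3 and believe that it was complying with the protocol. A participant recorded as off study has no reason to receive the follow-up calls.

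Kaplan-Meier assumes that a censored participant has the same future risk of death as those still followed. A participant removed because the disease has progressed will usually be at higher risk, so OS would be biased upward. LFS, which counts AML or death from any cause, is exposed in the same way. With cohorts of 32 and 25, few deaths would be left for the estimate.

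The expedited-reporting waiver in Section 8.4 also depends on this follow-up. It exempts phase II deaths and hospitalisations due to progression because the study captures them as endpoints, and removal at progression would weaken that ground.

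The 10.1 safety window is a separate and smaller matter. It leaves unclear whether events after progression but within 100 days of the last dose count towards the phase II safety endpoint.

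**Working it through.** The plan gives no figure on this point to reproduce. The check sets the passages side by side and then sizes a literal reading.

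**1. Passages**

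| Question | Cuts off at progression | Continues past progression |
|---|---|---|
| Study status | 6.3 | 3.8.1 with 3.8.2; 3.1; 3.4; Appendix F |
| OS and LFS definition | none | 10.1, 10.4.3 |
| Phase II safety endpoint | 10.1 safety row | 3.8, 6.1, 8.5 (100 days after last dose) |

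Only 6.3 threatens OS and LFS. The 10.1 cut-off applies to the safety row (and to the response window), not to the survival endpoints.

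**2. OS if 6.3 were followed literally**

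Assumed monthly hazards, not from the documents: death before progression m0 = 0.02, progression λ = 0.05, death after progression m1 = 0.10. Write a = λ + m0 = 0.07.

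- True survival: S(t) = exp(−at) + [λ/(a − m1)]·[exp(−m1·t) − exp(−at)]. With these inputs, S(t) = 2.667·exp(−0.07t) − 1.667·exp(−0.10t). Setting S(t) = 0.5 gives t = 17.3 months.
- Every progression censored: only m0 is seen, so the Kaplan-Meier median is ln 2 / 0.02 = 34.7 months. The share of deaths observed is m0/a = 0.02/0.07 = 29%.
- Only progressions in the first c months censored: the estimate is exp(−m0·c)·S(t − c) for t > c.
  - c = 6: exp(−0.12) = 0.887, so S(t − 6) must equal 0.5/0.887 = 0.564. This gives t − 6 = 14.9 and a median of 20.9 months.
  - c = 12: exp(−0.24) = 0.787, so S(t − 12) must equal 0.636. This gives t − 12 = 12.5 and a median of 24.5 months.
- Equal death hazards (m1 = m0): S(t) = exp(−m0·t), so the median is unbiased and only precision is lost.

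**3. Range, scaled to the protocol's background medians**

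Section 1.2.1 gives median OS of 1.5 years (higher risk) and 5.9 years (lower risk). Assume that 20% to 50% of deaths occur without prior progression, that the death hazard after progression is 2 to 4 times that before it, and that every progression is censored. A true 1.5 years would then be estimated at 1.8 to 3.2 years, and a true 5.9 years at 7.1 to 12.6 years. These are upper-end cases, because all progressions are censored. At a hazard ratio of 1 the medians stay at 1.5 and 5.9, but 50% to 80% of deaths would go unobserved.

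**4. Safety window**

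BMS-986253 is given on Days 1 and 15 (Section 3.1), and scheduled marrows fall on Day 28 ± 3 (Section 3.4). Days since the last dose at the marrow: 25 − 15 = 10, 28 − 15 = 13, 31 − 15 = 16. Days of the 100 outside the 10.1 endpoint: 90, 87 and 84.

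**The case against.** The strongest reply is that the protocol read as a whole plans to follow these participants. The schema note in Section 3.1 treats progression as the end of treatment. Section 3.4 then gives an End of Treatment visit and years of calls, and Appendix F records later therapy and AML. A reader might infer from 6.3 that the trial cuts off OS and LFS at progression. The documents do not support that reading: one sentence in the response-criteria section is out of line with all the operational sections.

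The 6.3 trigger is also limited to interim marrow results. In phase II, marrows are required after cycles 2 and 6 and for aplasia or suspected progression. Progression learned by phone after treatment has stopped falls outside it. Censoring every progression is therefore a ceiling, which is why the working also shows cut-offs at 6 and 12 months. Responders stay on treatment until progression, so the literal-reading bias lies somewhere between those results and the ceiling.

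On safety, a reader might infer that participants who progress contribute none of the 100 days, or that their later events are lost. Neither holds. The 10 to 16 days before a scheduled marrow count, and 6.1 and 8.5 still require the events to be collected. Sections 10.3.1 and 10.4.4 carry no progression cut-off either.

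These points narrow the concern to a contradiction with a risk of lost follow-up. They do not remove it, because 6.3 still gives the wrong status in plain terms.

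**Conclusion.** The point stands as an internal contradiction that should be corrected, not as an established loss of data. Section 6.3 conflicts with 3.1, 3.4, 3.8.1, 3.8.2 and Appendix F. If 6.3 were followed, OS and LFS would be informatively censored at marrow-detected progression. In the illustration, a true median OS of about 17 months becomes about 21 (first 6 months only) to 35 (all progressions). That range rests on assumed constant hazards and vanishes if death hazards before and after progression are equal. If the other sections are followed, there is no bias.

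Separately, the 10.1 phase II safety window conflicts with 3.8, 6.1 and 8.5. For progression found at a scheduled marrow after a Day 15 dose, 84 to 90 of the 100 days fall outside the stated endpoint, although the data would be collected. The textual conflicts are certain; the size of any OS bias is not.

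**What to change.** - **Section 6.3:** reconcile with 3.8.1 and 3.8.2, so that progression changes treatment status only. State that OS, LFS and safety follow-up continue under 3.1, 3.4 and 6.1.
- **Section 10.1, phase II safety row:** align the window with 6.1, from first dose through 100 days after the last dose.
- **Section 3.4, for completeness:** name LFS among the follow-up statuses. It now lists overall, event-free and progression-free survival only, although Appendix F already collects the AML date.

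The cost is wording in an amendment. No visit, assessment, data item or sample size changes, because the follow-up calls and the 100-day collection are already planned. If anyone has already been recorded as off study under 6.3, check their status and resume follow-up where consent allows.
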